We believe TXA has the potential to assist in perioperative control of hemorrhage during burn excision surgery leading to decreased blood loss and smaller transfusion rates. These potential improvements in care may translate into decreased surgical complications and a potential reduction in hospital stay and overall costs.

5. Setting of the Research:

Spectrum Health Butterworth Campus

6. Resources Available to Conduct this Research:

The Spectrum Health Regional Burn Center admits nearly 120 patients each year. Many of these patients require surgical management of their sustained injuries. Study personnel will

include attending burn surgeons and surgical residents with experience in surgical research and knowledge of surgical outcome measures. In addition, the Spectrum Health Office of Clinical Research Operations (OCRO) staff will assist with the informed consent process and subject enrollment, data collection and management, Institutional Review Board (IRB) communication and continuing renewal submission, ongoing subject management, and maintenance of the regulatory files and essential documentation for the study.

7. Study Design:

a. Recruitment Methods

Potential subjects will be recruited during the preoperative period for a planned procedure with any of the burn attending surgeons. A member of the Spectrum Health OCRO will obtain informed consent. This will take place in a private consultation room to ensure privacy and should take approximately 45-60 minutes. In order to minimize coercion, it will be made very clear to patients that their participation is strictly voluntary and that choosing not to participate will in no way affect their care at Spectrum Health.

Study Subjects

Potential subjects include all patients scheduled to undergo burn excision surgery with a deep partial or full thickness burn wound area of at least 350 cm² that meet all of the inclusion criteria, and none of the exclusion criteria. For a procedure to be included within the study, 96 hours must have elapsed since the previous procedure in which the patient was randomized to drug or placebo. If the patient has undergone a procedure outside the scope of this study, the 96-hour waiting period does not apply.

i. Inclusion Criteria

- Subjects undergoing burn excision surgery for standard of care purposes (to include: greater than or equal to 350 cm² of full thickness or deep partial thickness burns)
- Male or female \geq 18 years of age

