- Subject or subject's medical decision maker agrees to participate in this study and provides informed consent

ii. Exclusion Criteria

- Subjects with a history of hypercoagulopathy, deep vein thrombosis or pulmonary embolism
- Baseline creatinine level greater than 2.83 mg/dL
- Subjects with known hypersensitivity to tranexamic acid
- Patients with acquired defective color vision
- Patients with subarachnoid hemorrhage
- Children
- Pregnant women
- Prisoners

b. Study Endpoints

The primary outcome measures will be operative blood loss (measured and calculated) and red blood cell transfusion rates in subjects undergoing the eligible procedures. Secondary outcome measures will include total hospital length of stay, wound complication, transfusion reactions, and skin graft survival.

c. Procedures Involved in the Research

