The study design will be a randomized, double-blinded, placebo-controlled trial, with the randomization to occur on a per procedure basis. Following satisfaction of inclusion/exclusion criteria and enrollment into the study by the Spectrum Health OCRO research staff, the subject and each procedure the patient undergoes will be assigned a study number. A single consent will be obtained for randomization of each procedure that a patient may undergo meeting inclusion criteria for the study. A single study participant could potentially be randomized to both treatments of the study if that participant undergoes two or more procedures. Each procedure a participating subject undergoes will be randomized based on a predetermined randomization schedule, created by an independent statistician at Grand Rapids Medical Education Partners (GRMEP) research department. The randomization schedule will be held by the pharmacists and checked prior to each procedure to determine the appropriate treatment (placebo or TXA). Surgical timing will be coordinated with the OCRO. The study participants will receive preoperative intravenous TXA or Normosol as placebo treatment. The preparation will be indistinguishable by nursing, surgical, or anesthesia staff. The TXA procedures will receive a 1000 mg dose immediately preceding surgical incision administered by the anesthesia provider, while the placebo procedures will receive an equivalent volume of Normosol. The dose will be administered via intravenous piggyback over 15 minutes. Operative details will be recorded including procedure performed, IV fluids received, estimated blood loss, lowest recorded body temperature, and transfused blood products. Perioperative hemoglobin level data will also be collected. Standard daily laboratory measurements will continue unless clinical conditions necessitate more frequent monitoring, per standard practice. Transfusion will take place for hemoglobin levels < 7.0 g/dL or hemoglobin level < 10 g/dL with clinical symptoms indicating need for transfusion, per standard practice. Final decision on transfusion will be made according to the staff surgeon's discretion.

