It is anticipated that each patient will receive an average of three major surgical procedures during the treatment of their burn injury. The number of procedures may range from a single procedure to greater than 6 procedures for an individual patient depending on the extent of their injury. The time between subsequent procedures typically ranges from ten days to several weeks. Prior to each procedure, the patient will be re-randomized to receive TXA or placebo.

Data to be recorded includes patient demographics (age, sex, height, weight), burn injury characteristics (total body surface area, location, depth of burn), hospital admission date, hospital discharge date, past medical history, past surgical history, medications, and laboratory values. Data from operative records will include procedure date, procedure performed, wound measurements, lowest body temperature, operative blood loss, operative time, amount of fluid received, and intraoperative transfusion requirements. Postoperative data to be collected includes hemoglobin and hematocrit levels, transfusion requirements, surgical complications, skin graft survival (%), thromboembolic events, and length of hospital stay.

d. Data Management

The Spectrum Health OCRO research staff will collect outcome data at the time of each surgical procedure. Data will be stored in a password-protected REDCap

database. The OCRO will also keep a secure record of the procedures randomized to the TXA and placebo arms, which will be blinded from the study personnel.

e. Provisions to Monitor the Data for the Safety of Subjects

Adverse events including infections, allergic reactions, graft loss, respiratory failure, anaphylaxis, thromboembolic events and development of acute renal failure will be monitored and recorded at the time of occurrence by the Spectrum Health OCRO research staff. In the event an increased number of unanticipated events occur, the study will be temporarily stopped pending review. A review of unblinded data will be performed by an independent clinician and statistician at Grand Rapids Medical Education Partners to determine the need to discontinue or resume the study. If a significant increase in adverse events is noted in the treatment arm related to the study drug, the trial will be terminated. Decisions resulting from the review will be discussed with the primary investigator.

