Interim reviews of unblinded data for statistically significant findings will be performed by an independent clinician, pharmacist, and statistician after the first 80 procedures have been completed. Findings will be reviewed with the investigators, and decisions will be made as to whether or not the research study continues. These interim reviews and outcomes will be reported to the IRB.

f. Withdrawal of Subjects

Subjects will be withdrawn from the study if they experience an adverse drug reaction defined as anaphylaxis. Other potential side effects such as nausea, vomiting, or diarrhea will be treated symptomatically per standard of care. If refractory to standard treatment for these side effects, subjects will be withdrawn from the study. Subjects experiencing any thrombotic event prior to completion of study drug dosing schedule will be withdrawn from study. Subjects may choose at any time to voluntarily withdraw from the study. If subjects choose to withdraw, No further data will be collected. Data already collected will be included in the study.

The primary investigator may remove a subject at any time from this research study if it is felt to be in the best interest of the subject.

8. Statistical Plan

a. Sample Size Determination

The primary outcome variable for the study is transfusion following a procedure. The analysis will be performed using generalized estimating equations (GEEs), as each individual may have multiple surgical procedures that may be randomized to either the control or TXA treatment prior to EACH procedure. An initial assessment for sample size for a McNemar test, assuming that the transfusion rate following a control procedure is 50%, the rate following a TXA procedure is 30%, $\alpha = 0.05$ and $\beta = 0.20$, indicates that 61 subjects would be needed. The control transfusion rate is based upon previous data at Spectrum Health, while the difference of 20 percentage points is based upon our estimate of what constitutes a clinically important effect. Due to the use of GEE for the analysis, a correction factor is needed.¹⁷ From previous data from the Spectrum Health Burn Unit, we assume that there will be three procedures per patient. If we further assume that the intraclass correlation coefficient = 0.8 (postulated correlation of repeated measurements), we will be able to show a statistically significant effect with 53 subjects. With an average of 3 procedures per patient, the total procedures will be 159.

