b. **Statistical Methods**

Summary statistics will be calculated. Quantitative data will be expressed as the mean±SEM and nominal data will be expressed as a percentage. Comparisons between groups for quantitative variables will be performed using the t-test. Nominal variables will be evaluated using the χ^2 test. The relationship between TXA administration and transfusion will be determined using GEE. Significance will be assessed at $p<0.05$. Analyses will be performed using intention to treat.

9. Risks to Subjects

TXA is an FDA approved medication. The safety of TXA has been demonstrated in a meta-analysis of the off-label use of TXA in the perioperative period. A theoretical risk of thromboembolic events exists, though no significant adverse outcomes have been reported with the proposed dosing schedule. Reported side effects include nausea, vomiting, diarrhea, and dizziness. Uncommon side effects include allergic dermatitis, giddiness, and hypotension. Rare side effects include blood clots, convulsions, and visual changes.

10. Potential Benefits to Subjects

Potential benefits include decreased surgical blood loss resulting in decreased transfusion requirements. Transfusion of packed red blood cells has been associated with numerous potential adverse events. In addition, decreased overall hospital cost may occur if the study subjects experience decreased complication rates.

11. Provisions to Protect the Privacy Interests of Subjects

The study, potential risks and benefits of treatment will be discussed extensively with each potential subject preoperatively in a private space. Any questions they have will be answered accordingly. Reported data will not contain identifiable information. Patient consent and all other research related activities will take place in a private exam room.

12. Provisions to Maintain the Confidentiality of Data

Identifiable study data will be kept in a secure password-protected file or locked cabinets by the Spectrum Health OCRO. The Spectrum Health OCRO will have record of the randomization of each individual subject stored in a controlled, secure area.

13. Medical Care and Compensation for Injury

Any medical or surgical complications experienced relative to this research will be treated in accordance with current standards of care. No study funds have been set aside to compensate subjects for injury.

14. Cost to Subjects

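### Operative blood loss is left to a t-test that ignores repeated procedures per patient, although the plan's reason for using GEE applies to it equally

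*Combined protocol and SAP*

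**What the plan says.** Section 7b (Study Endpoints) gives two primary outcomes: "The primary outcome measures will be operative blood loss (measured and calculated) and red blood cell transfusion rates". Section 8a (Sample Size Determination) names one: "The primary outcome variable for the study is transfusion following a procedure".

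Randomization is by procedure. Section 7c allows one patient to contribute to both arms: "A single study participant could potentially be randomized to both treatments of the study if that participant undergoes two or more procedures". It expects about three procedures each, but "The number of procedures may range from a single procedure to greater than 6 procedures for an individual patient". Blood loss is recorded at every operation (7c, 7d).

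Section 8a explains the choice of GEE by this structure: "as each individual may have multiple surgical procedures that may be randomized to either the control or TXA treatment". Section 8b (Statistical Methods) then gives GEE a narrow scope: "The relationship between TXA administration and transfusion will be determined using GEE". For continuous data it says: "Comparisons between groups for quantitative variables will be performed using the t-test". Summaries of quantitative data are to be mean±SEM.

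Section 8b does not mention blood loss by name. Blood loss comes under the t-test because it is quantitative and no other method is given for it. No section provides a paired, mixed-model, GEE or cluster-robust analysis for any continuous outcome.

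**The concern.** The argument in 8a for GEE concerns how the data arise: several procedures from the same patient, each allocated separately. That holds for blood loss as much as for transfusion. A procedure-level t-test treats all procedures as unrelated.

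The usual worry with clustered data is false positives. That is not the issue here, because treatment varies within patients. The issue is precision: re-randomizing within patients lets each patient act partly as their own control, and the t-test does not use this. In addition, an SEM for each arm computed with procedures as n overstates how well each arm mean is known.

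**Working it through.** **The plan's own figure.** From 8a: 61 subjects before correction, three procedures per patient, ICC 0.8. Then 61 × [1 + (3 − 1) × 0.8] / 3 = 61 × 2.6 / 3 = 52.87, rounded up to 53 patients; 53 × 3 = 159 procedures. Both stated figures reproduce, so 53 × 3 is used below.

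**Assumptions.** The documents give no SD, target difference or ICC for blood loss, and no allocation ratio or blocking. I assume independent 1:1 allocation per procedure, normal outcomes with total variance 1, a 0.4 SD effect for illustration, and ICC ρ of 0.2, 0.4, 0.5 and 0.8. The last is the value 8a postulates for the transfusion-based sample size.

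**Why the t-test stays valid.** Under independent 1:1 allocation, two procedures from one patient are as likely to fall in the same arm as in opposite arms. Their covariances cancel on average in the difference of arm means, so the t-test's standard error is about right.

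**Formulas for three procedures per patient**

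- Efficiency relative to the t-test: (1 + ρ) / [(1 + 2ρ)(1 − ρ)]. At ρ = 0.5: 1.5 / (2.0 × 0.5) = 1.50.
- Difference detectable with 80% power, two-sided 5%: 2.8016 × 2 / √(159 × efficiency). For the t-test (efficiency 1): 5.6032 / 12.61 = 0.444 SD.
- Arm SEM with procedures as n, relative to the true one: each procedure has on average one other procedure by the same patient in the same arm, so the ratio is 1/√(1 + ρ).

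| ICC | 0.2 | 0.4 | 0.5 | 0.8 |
|---|---|---|---|---|
| Efficiency | 1.07 | 1.30 | 1.50 | 3.46 |
| Detectable difference, SD (t-test 0.44) | 0.43 | 0.39 | 0.36 | 0.24 |
| SEM ratio | 0.913 | 0.845 | 0.816 | 0.745 |

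**Simulation: 53 × 3, 5,000 runs per setting**

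| Power at 0.4 SD, % (null rejection, %) | ICC 0.2 | 0.4 | 0.5 | 0.8 |
|---|---|---|---|---|
| t-test | 70.0 (5.2) | 70.6 (5.2) | 70.8 (4.8) | 71.0 (5.6) |
| GEE, independence | 71.5 (6.1) | 72.7 (6.2) | 72.6 (5.4) | 73.0 (6.5) |
| GEE, exchangeable, Mancl-DeRouen SE | 71.5 (5.2) | 80.8 (4.5) | 85.1 (4.5) | 99.5 (4.9) |
| Patient random intercept | 73.2 (5.5) | 82.2 (4.6) | 86.3 (4.4) | 99.5 (5.1) |

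The small apparent gain of independence GEE comes with null rejection above 5%, so it is essentially no gain. Exchangeable GEE with an uncorrected robust SE rejected 5.7–6.5% of null runs.

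**Other settings**

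- One to six procedures per patient (assumed 25/20/20/15/10/10%, mean 2.95, 54 patients): t-test 70.3/70.8/70.1/72.6%; corrected exchangeable GEE 71.8/80.7/84.8/99.5%.
- Allocation in blocks of four across procedures: t-test 71–72%; corrected GEE 73.0/80.5/85.3/99.5%.
- Allocation balanced within patient: the t-test becomes conservative, with null rejection 3.7/2.7/1.9/0.5%.
- Whole patients allocated to one arm: t-test null rejection is 9.5% at ICC 0.2 and 23% at 0.8. This is not the trial's design.

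**The case against.** The planned test is valid under the assumed allocation, so the point is about efficiency, not wrong inference. That is correct, and no bias or inflation is claimed.

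The gain depends on an ICC that the documents do not give. At 0.2 the corrected GEE gains only 1.5 percentage points (71.5% against 70.0%). The 0.8 in 8a is postulated and belongs to transfusion. Section 4 also describes blood loss as depending on the area debrided, which can differ between one patient's operations and could lower the raw ICC. This stands. The high confidence attaches to the gap in the plan, not to any one size of loss.

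If transfusion alone is primary, as 8a has it, the loss falls on a supporting outcome. The gap remains but matters less.

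A correlation-aware analysis has two real drawbacks:

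- **Weighting.** With the assumed one-to-six distribution, single-procedure patients supply 0.25 / 2.95 = 8.5% of the t-test estimate but 7.8/6.4/5.5/2.4% under exchangeable weighting. If the effect grew in proportion to the number of procedures (an assumption), the estimate would shift by 1.4/3.7/5.0/9.1%.
- **Carry-over.** A carry-over κ to the next procedure biases the estimate by −(2/3) × ρ/(1 + ρ) × κ, that is −0.11/−0.19/−0.22/−0.30 κ. With κ at 10% of the effect, the estimate shrinks by about 1–3%. The t-test avoids this. Section 7a requires a gap: "96 hours must have elapsed since the previous procedure in which the patient was randomized to drug or placebo". Section 7c expects intervals of ten days or longer.

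Both are modest, and a retained t-test would reveal either.

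**Conclusion.** The concern holds. Section 8a's reason for GEE covers blood loss, but 8b leaves blood loss to a t-test, and no other section supplies a clustered method. Under independent 1:1 allocation the t-test is valid but inefficient. A model that uses the within-patient correlation is worth 1.07 to 3.46 times the procedures as the ICC runs from 0.2 to 0.8, and the detectable difference falls from 0.44 SD to between 0.43 and 0.24 SD. Arm SEMs based on procedures are 9–25% too small; this affects the summaries, not the between-arm test. These sizes rest on three procedures per patient, 159 procedures and assumed ICCs, and the power figures also on an assumed 0.4 SD effect. This is an inexpensive improvement that should be made, and it matters most if blood loss is indeed primary.

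**What to change.** In 8b:

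1. Replace the t-test for blood loss with a linear mixed model with a patient random intercept, or with identity-link GEE using an exchangeable working correlation and a small-sample-corrected robust SE (for example Mancl-DeRouen).
2. Name the working correlation. None is given even for the transfusion GEE, and independence would bring essentially no gain on blood loss.
3. Use the same patient-clustered approach for other per-procedure outcomes such as graft survival and wound complications. Length of stay is not a per-procedure outcome; state how it is attributed to an arm, or report it descriptively.
4. Report arm summaries with SDs or cluster-adjusted SEs.
5. Keep the t-test, or a model that adds the previous procedure's allocation, as a sensitivity analysis. The added term removes the carry-over bias for a 2–7% larger SE.
6. Reconcile 7b and 8a on whether blood loss is primary.

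Adjusting for the wound measurements already collected (7c) is worth considering, but its benefit was not quantified here.

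The cost is SAP wording and slightly more analysis, with no extra patients or data. The price is reliance on a working correlation model, the weighting and carry-over sensitivities described above, and almost no gain if the ICC is near 0.2.

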NCT02753816

Document Date: 07/10/2018

1. TXA Protocol Title: The effect of tranexamic acid on blood loss and transfusion rates in burn wound surgery – A randomized, double-blinded placebo-controlled trial.

2. Version Date: 7/10/18

3. Objectives:

- To determine the impact of perioperative administration of tranexamic acid on intra-operative blood loss and post-operative transfusion rates in burn wound surgery.

4. Background:

An estimated 40,000 patients were hospitalized for burn related injuries in 2014.¹ Many of these patients required surgical excision and grafting. Early excision of burn eschar has been shown to reduce mortality, hospital stay, and time away from work. However, intraoperative blood loss and blood product transfusion rates have been shown to be higher.^{2,3} Tangential excision of burns often causes large losses of blood, which have been estimated between 0.4 ml/cm² to 0.75 ml/cm² of debridement depending on timing of excision.⁴ There are many techniques that have been described to help reduce the loss of blood in burn surgery. These include timing of excision, maintaining euthermia, extremity tourniquet control, dilute epinephrine tumescent infiltration, and topical application of epinephrine and thrombin.^{5,6}

Tranexamic acid (TXA) has been used as an adjuvant to reduce bleeding since the 1960's.⁷ TXA acts by competitively binding to plasminogen leading to inhibition of its activation to plasmin. This is thought to inhibit fibrinolysis, maintain formed clot, and decrease perioperative bleeding.⁸

Topical and intravenous uses of TXA have been studied in a variety of surgical specialties, including orthopedic surgery,⁹ oral surgery,¹⁰ cardiovascular surgery,¹¹ trauma,¹² as well as gynecology.⁷ Impact on blood loss and decreased transfusion needs have been promising. Very little data exist on the use of TXA in burn surgery with only one case report and one prospective trial published.^{13,14} Although a small sample size was used, results were encouraging for decreasing intraoperative blood loss. The effect on perioperative blood transfusion was not addressed in this study.

Due to inhibition of fibrinolysis, a theoretical risk of venous thromboembolic (VTE) events is at the forefront for concern. Numerous studies have shown no increase in VTE events with perioperative use of TXA.^{9,15} Although the reasons are unclear, incidence of VTE within the burn population are quite low (0.8%) compared to many inpatient populations.¹⁶

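### Operative blood loss, named a primary outcome in section 7b, has only an unadjusted t-test; adjusting for excised area with patient as the cluster would be a cheap gain in precision

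*Combined protocol and SAP*

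**What the plan says.** - **Status of blood loss.** Section 7b (Study Endpoints) reads: "The primary outcome measures will be operative blood loss (measured and calculated) and red blood cell transfusion rates in subjects undergoing the eligible procedures". Section 8a (Sample Size Determination): "The primary outcome variable for the study is transfusion following a procedure". Section 8a sizes transfusion only.
- **Analysis.** Section 8b (Statistical Methods) has one rule for every quantitative variable: "Comparisons between groups for quantitative variables will be performed using the t-test". The clustered model is named for the other outcome: "The relationship between TXA administration and transfusion will be determined using GEE". No covariate, transformation or per-area scaling is mentioned.
- **Loss and area.** Section 4 (Background) describes the losses from tangential excision, "which have been estimated between 0.4 ml/cm² to 0.75 ml/cm² of debridement depending on timing of excision".
- **Range of area.** Section 7a (Study Subjects) requires a "deep partial or full thickness burn wound area of at least 350 cm²" and sets no upper limit.
- **Data.** Section 7c says that operative records will supply "procedure date, procedure performed, wound measurements, lowest body temperature, operative blood loss" and other items. No planned analysis uses the wound measurements.

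**The concern.** If loss is roughly area times a rate per cm², a comparison in mL carries the spread of wound size in its error term. Randomisation balances area on average, so the comparison stays unbiased, but area remains as noise that a recorded covariate could remove. The t-test's robustness at about 80 procedures per arm protects the type I error. It does not restore the lost precision.

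The t-test also takes no account of several procedures coming from one patient, a feature that section 8a recognises for transfusion.

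At stake is whether a real proportional reduction in an outcome that section 7b calls primary is missed, or estimated so loosely that a few very large excisions decide the result.

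**Working it through.** **The plan's own figure.** Section 8a starts from 61 subjects, with three procedures each and an intraclass correlation of 0.8. The correction N × [1 + (T − 1) × ICC] / T gives 61 × [1 + 2 × 0.8] / 3 = 61 × 2.6 / 3 = 52.9, so 53 subjects, and 53 × 3 = 159 procedures. This reproduces the plan. At 1:1 allocation (the ratio is not stated) there are about 80 procedures per arm. There is no corresponding figure for blood loss to reproduce.

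**Assumptions not in the documents.** A 25% reduction; area and loss per cm² both lognormal; SD of log area 0.5 or 0.9; residual SD of log loss per cm² 0.5 or 0.7; two-sided 0.05; procedures independent; the 350 cm² floor not imposed.

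**Log loss per cm².** The effect is −ln(0.75) = 0.288 and its standard error is s × √(2/80).
- s = 0.5: 0.288 / 0.0791 = 3.64, power 95%.
- s = 0.7: 0.288 / 0.1107 = 2.60, power 73%.

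**Loss in mL.** With s² = (SD log area)² + (residual SD)², the squared coefficient of variation is CV² = exp(s²) − 1. In units of the control mean, the standard error is √[CV² × (1 + 0.75²) / 80].
- SDs 0.5 and 0.5: CV² = exp(0.50) − 1 = 0.649; standard error 0.1126; 0.25 / 0.1126 = 2.22; power about 60% by the normal approximation, 62% by simulation.
- SDs 0.9 and 0.7: CV² = exp(1.30) − 1 = 2.669; standard error 0.2283; 0.25 / 0.2283 = 1.09; power about 19% by the approximation, 22% by simulation.

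**All four settings.** The last power column is from the closed form; the other power columns are simulated. Area share is (SD log area)² / s². Power lost is 1 − (power on mL) / (power on log loss per cm²).

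| SD log area | Residual SD | Area share of log variance | t-test, mL | t-test, log mL | t-test, mL/cm² | t-test, log(mL/cm²) | Power lost |
|---|---|---|---|---|---|---|---|
| 0.5 | 0.5 | 50% | 62% | 72% | 92% | 95% | 35% |
| 0.5 | 0.7 | 34% | 43% | 56% | 63% | 73% | 41% |
| 0.9 | 0.5 | 76% | 28% | 42% | 93% | 95% | 71% |
| 0.9 | 0.7 | 62% | 22% | 36% | 63% | 73% | 70% |

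**Check with clustered data.** A second simulation used 53 patients with three procedures each, within-patient correlation 0.3 for area and for rate, mean area 1000 cm², and areas below 350 cm² set to 350. It compared the t-test on mL with a regression of log loss on treatment and log area. With residual CV 0.5 except where stated:
- 20% reduction, area CV 0.8: 29% v 82%.
- 25% reduction, area CV 0.4: 76% v 96%.
- 25% reduction, area CV 0.8: 46% v 97%.
- 30% reduction, area CV 0.4, residual CV 0.3: 99% v 100%.

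Over the whole grid the t-test on mL had 15% to 99% power and the adjusted analysis 59% to 100%. The t-test on mL was never the better of the two. Neither simulation fitted a clustered model, so these figures show the gain from area and not any further gain from modelling the patient.

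**The case against.** The strongest reply has four parts.

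1. **The scale is unstated.** Section 8b names a test, not a unit. Loss per cm², the scale of the Background, is compatible with it. A plain t-test on mL/cm² already has 63% to 93% power in the settings above, so most of the gain could be had within the stated test. This stands. A reader might infer that the plan commits to mL; the text is only silent.
2. **Transfusion may be the only primary outcome.** Section 8a says so and sizes nothing else. No target reduction or power is claimed for blood loss, so no promised power is broken. This also stands, and it limits the weight of the point. It does not remove the gain, which would be equally available for a secondary outcome.
3. **The unadjusted mean difference is valid and in familiar units.** True, and a ratio of geometric means is a different estimand. A reader who prefers mL can still adjust: with clustered data, a 25% reduction, area CV 0.8 and residual CV 0.5, regressing loss in mL on treatment and area had 82% power, against 46% unadjusted.
4. **Wound measurements may not be area excised.** With staged excision they can differ. This is a condition on the fix.

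A reader might also infer that ignoring repeated procedures inflates the type I error. The documents do not show that. Section 7c randomises each procedure, so treatment varies within patients, and the main expected cost of ignoring the patient is precision.

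**Conclusion.** The point holds as a cheap improvement. As written, blood loss would get an unadjusted t-test, with no use of area and no allowance for repeated procedures. Under the stated assumptions, a t-test on mL would forfeit about 35% to 41% of the attainable power when areas vary modestly and about 70% when they vary widely.

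Two stronger readings are not supported. One is that most of the power is lost whatever the setting. That depends on area spread, residual spread and effect size, none of which the documents give; at a 30% reduction with area CV 0.4 to 0.6, the clustered-data check put the loss at about 1% to 34%. The other is that wound size accounts for most of the variation in loss. Under these assumptions its share of log variance runs from 34% to 76%. The Background's range of 0.4 to 0.75 mL/cm² is attributed to timing of excision and does not describe the spread of area.

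**What to change.** - Reconcile sections 7b and 8a on whether blood loss is primary.
- In section 8b, state the unit for blood loss and which of the measured and calculated values is analysed.
- Prespecify an analysis of blood loss with area excised at that procedure as covariate, in a GEE or mixed model with patient as the cluster. Preferably model log loss on log area and report the ratio of geometric means with its 95% CI.
- Keep the unadjusted mean difference in mL as a supplement.
- Because the dose precedes incision, extent of excision could in principle respond to bleeding. A sensitivity analysis using the wound area assessed for eligibility would cover this.

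The cost is a few sentences of analysis plan, provided that the recorded wound measurements capture the area excised at each procedure; if they do not, the data form needs one more item. The main effect becomes a ratio, and zero losses need a stated rule before unblinding.
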